# 12. Data and Specimen Banking\*

Any data collected by this study may be used for future research. The PI or another approved member of the study team will determine who is allowed to access this data. It may include collaborators or entities external to UMMS.

ECG and pulse data from all smartphones and watches will be sent to a secure server managed by UConn's information technology services. The data will not be transmitted with participant name, DOB, or MRN. The Pulsewatch system will upload data when prompted by participants during Aim 3 or by a trained study staff member during the 14-day study visit. This data management system is encrypted. Data storage capacity on the Pulsewatch is nearly 14 days at the above noted sampling rates for PPG. Thus, pulse data will be safely stored and will be retrieved when the Pulsewatch is returned for Aim 2 after 14 days. All ECG and pulse data will be password protected and encrypted so that only research personnel can access stored data. Once smartwatches are returned, we will have the study coordinator "push" pulse and ECG data from the smartwatch and adherence/annotation data from the smartphone. If the smartphone is lost, however, we will extract the latest adherence and annotation data and then remotely delete the File Store. This protocol protects participants' confidentiality in addition to the data encryption and password protection. We have the programming expertise necessary to carry out these operations.

The AliveCor Kardia platform used to store ECG data from the AliveCor ECG system is a HIPAA-compliant, HL7 compliant service used by the Cleveland Clinic, UMMMC, and other services for clinical grade ECG storage and analysis. This protocol protects participants' confidentiality in addition to the robust means of data encryption and password protection. We will upload only ECGs linked to participant IDs. ECGs will be reviewed within 3 days of uploading by study staff. The platform will be checked daily on normal business days to observe any tracking completed by participants.

The Cardiac Insight patch data will be transferred to the PI via a summary report for review. This will be reviewed and stored in a locked, secure space. The data from the Cardiac Insight

patches will be de-identified, containing only a participant study ID #. The raw data and digital summary reports will be stored on secure UMMS HIPPAA-compliant servers. Similar to the watch pulse and ECG data, the Cardiac Insight ECG data will also be uploaded to the same secure server managed by UConn's information technology services. The data will not be transmitted with participant name, DOB, or MRN.

Focus group and exit interview recordings, Hack-a-thon materials, and questionnaires (baseline and follow-up) will be stored in a digital format (using the nVivo system for audio recordings and the RedCAP system for questionnaire data) as well as on paper. All digital data will be password protected and encrypted so that only research personnel can access stored data using the RedCAP system. All paper questionnaires, consents, etc., will be stored in a locked, secure UMMS space.

Screening documents to identify patients to approach for the study will be stored in the Redcap File Repository and deleted when we have finished enrolling participants. We will destroy the master file of the identifiers of the enrolled participants 5 years after all data analysis is completed. De-identified data coded with the Subject ID of participants will be retained indefinitely to be reviewed for future publication use. Any paper or physical copies will be stored in locked spaces. Audio recordings will be deleted after a research staff member has completed the transcription process and quality check process. Transcription will be de-identified, protecting confidentiality by replacing participants' names with study IDs. The master file that links the participant to the identifiable information will be in a secure database (RedCAP) and only limited research personnel will have access to this information to help protect participants' personal information. Please see our HIPAA Waiver, which is in eIRB.

## 13. Data analysis and Management\*

## **Overall Data Management:**

Each participant enrolled in this study will receive a participant ID to ensure that limited personal information of our participants is not accessed unnecessarily. Our study team, including the study PI, will meet with an independent monitor quarterly to ensure adequacy of human subject's protections, including participant privacy.

For all patient participants, sociodemographic, clinical, laboratory, and medical care information will be abstracted from records into a web-based centralized data repository, which was developed and is being used in SAGE-AF. As in our prior studies, we will abstract data on history of TIA/stroke, stroke severity, and clinical variables necessary to derive the CHA2DS2VASc (stroke) risk scores. We will abstract use of medications (e.g., beta-blockers) known to influence vulnerability to AF. Data from health records will be imported to our data repository as in the SAGE-AF study.

Data streams will be merged into the Pulsewatch master database that will include audio and digital information from focus groups, exit interviews, and questionnaires. AF rhythm status will be determined based on ECG data, and summary reports will be stored in the Pulsewatch master database utilizing our data system architecture similar to that used in SAGE-AF. Data acquisition and quality control processes will be the same. Unique, password-protected, registry websites assure consistent staff identification at entry. A data collection manual with coding

Pulsewatch ISP V 1.5 Docket#: H00016067

### PULSEWATCH INVESTIGATOR STUDY PLAN

[figure not shown]
instructions for each data item in SAGE-AF has been developed and will be updated for Pulsewatch.

Questionnaires will be available in a digital format on password protected iPads (using the REDCap system) as well as on paper copies. All laptops, desktops, and iPads that we use in this study will meet the UMMS encryption policy. All digital data will be password protected and encrypted so that only research personnel can access stored data using the REDCap system. All paper questionnaires, consents, etc., will be stored in a locked secure UMMS space. ECGs will be sent to the AliveCor Kardia Pro platform, a secure provider ECG management system. The AliveCor Kardia Pro platform is a HIPAA-compliant, HL7 compliant service used by the Cleveland Clinic and other services for clinical grade ECG storage and analysis. This protocol protects participants' confidentiality in addition to the robust means of data encryption and password protection.

Cardiac Insight patches have a module chip inside the sensor that stores the data being collected over the 14-days. Participants will be asked to bring back both patches at the end of the 14-day monitoring period to collect those modules for data collection. A trained study staff will remove the modules and place them into the Cardiac insight smart cable to be uploaded to a UMass Medical School server. The module will be labeled with the participants ID # and stored in a locked cabinet. The report will be read by a blinded Cardiologist for review. Details about the Cardiac Insight system can be found in the FDA approved Letter in eIRB (K162503 Cardiac Insight FDA) for the IRB to review. Similar to the watch pulse and ECG data, the Cardiac Insight ECG data will be uploaded to the same secure server managed by UConn's information technology services. The data will not be transmitted with participant name, DOB, or MRN.

#### Smartwatch Data:

We will reduce the potential for false positive AF detection from corrupted (MNA) or low amplitude (poor contact) PPG data using two methods. First, the Pulsewatch app will send a message to participants to remain still and perform a 30-sec ECG self-check (wrist electrode, high accuracy) should they have an AF episode detected. The second approach involves the cancellation of cyclical frequencies, seen in accelerometer data, from the PPG signal. This approach was recently developed in our lab and should allow us to use segments such as shown. We demonstrate this MN correction performance via a representative result from offline analysis of raw Samsung

watch data.(Looking at the figure above, the top panel of shows the comparison of our MN correction algorithm (green line) on raw data vs. Samsung's own embedded motion artifact correction algorithm (brown line). The black line is the reference heart rate from a 5-lead ECG. The bottom panel shows the raw PPG data recorded from the Samsung watch, and note MN artifacts starting at 100 seconds. The data were recorded during treadmill exercise (first 300 seconds), followed by 30 seconds of cool down, as well as with arm movements (up and down and shaking) on the side of the smartwatch. Despite the severity of the MN artifact, the estimated heart rates calculated by our algorithm closely follow the reference (black line) heart

rates. Thus, these 2 approaches can be effectively used to recover some data segments contaminated by MNA or by poor signal quality and correctly identify the presence or absence of AF. Once MN artifacts have been corrected, we will look at patterns to analyze pulse waveforms for AF detection, including discrimination of PVCs and PACs. The MNA and AF algorithms will be embedded using Samsung's Vobio API. Based on our pilot, we estimate 50% usable data during active periods and 90% during rest. The majority of the user's day will be at rest (sitting or sleeping), as older stroke patients typically perform limited exercise.

To fine tune and maximize the accuracy of our MNA algorithm, we will use data collected on AF subjects (Aims 2 and 3) using the Pulsewatch system. We will compare the performance of our MNA algorithm using the Pulsewatch signal to the simultaneous gold-standard Cardiac Insight patch. The data analysis and statistical evaluations will be similar to our recently published article on our MNA detection/reconstruction algorithm, but will also involve calculation of absolute error of the estimated heart rate via our algorithm to the reference Holter ECG-derived heart rate. Moreover, we will calculate sensitivity, specificity and accuracy of AF detection using our algorithm when compared to Cardiac Insight patch data.

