## 9. Study Timelines\*

The first year to 1.5 years of the study will be focused on achieving Aim I (**Part I – design of the application**). Focus groups will be scheduled on a rolling basis over Year 1 and will be strongly influenced by the coordinator and room availability, as well as participant preference. The Hack-

a-thon will also be scheduled at or around the end of Year 1 of the study (Spring 2019). Participants will be advised of when the event will be held.

Enrollment for Aims 2-3 (**Part II**) will begin in Year 2 and will run for 3 years. At enrollment, participants will be asked to use a cardiac monitor for 14 days and return for a study visit to evaluate device usability and accuracy. Thereafter, we will ask a randomly selected subsample to continue to use the device for an additional 30 days for a total of 44 days. We will hold additional semi-structured exit interviews for select Aim 2 intervention participants who used the Pulsewatch devices for 14 days.

Study Year	1				2				3				4			
Quarter	1	2	3	4	1	2	3	4	1	2	3	4	1	2	3	4
DEVELOPMENT/ENHANCEM	ИE	N٦	(/	۱in	n 1	)										
Formative patient focus groups & provider interviews																
Analysis of formative qualitative data																
"Hack-a-thon" Stakeholder- Agile Team Meeting																
Refine & Integrate AF, skin contact, & MNA algorithms																
EVALUATION/DEPLOYMENT (Aims 2 and 3)																
Smartwatch deployed in stroke population																
Follow-up interviews/exit interview assessment of app																
Data analysis																

The Pulsewatch study will be conducted over a 4-year period; see table below.

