#### PULSEWATCH INVESTIGATOR STUDY PLAN

The PI, Co-Is, 4 participants, 4 provider champions, and computer programmers and engineers from the University of Connecticut (UConn) will meet at the University of Massachusetts Medical School (UMMS) in a conference room to create the final Pulsewatch technology to be deployed in Aims 2 and 3. Modeled on "Hack-a-thons" in the software engineering industry, we will drive innovation by creating team synergy and accelerating product development. This meeting will likely occur in the Albert Sherman Center 7th floor conference room. Patient participants will receive parking vouchers and compensation. Providers will not be compensated. Light refreshments will be provided for all. The meeting will take place over a single day (8-hours) to accommodate the busy schedules of providers and participants. After the Hack-a-thon, the study team will meet to review and encode changes to the application.

The purpose of the Hack-a-thon meeting is to optimize the interactivity and usability of Pulsewatch, guided by information gleaned from focus groups. Using this format, end users (providers and patients) can suggest changes, and programmers will make modifications in realtime. Using a combination of focus groups and agile programming is an innovative as well as sound approach to designing apps. This event will be a critical aspect for Aims 2 and 3 to help develop the interface and management of the app for patients to use. At the Hack-a-thon, participants will be asked to use a prototype of the Pulsewatch app and the system, and then provide feedback on what they think of the system. Programmers will make modifications to the application in real time. While programmers are making those modifications, participants may take a break during the Hack-a-thon, and then come back at a later time during the event to see the final product.

The individuals who will be invited to this Hack-a-thon event will be participants and providers from the focus groups. At the focus groups, we will provide a fact sheet about the day-long Hack-a-thon and a contact sheet for people who may be interested in being invited. We will explain that they may accept or decline the invitation. (Please see Fact Sheet: Patient Hack-a-thon in our eIRB submission). Study staff will follow-up with interested participants and providers by telephone or email. Participants will have the option to opt-out or confirm their attendance at the Hack-a-thon.

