**Part II, Trial Phase-** The trial phase of the study will occur after the design and development of the Pulsewatch system (app and watch algorithms) is complete (Part I). For Aim 2 of Part II, participants will be randomized into either the intervention or control arm of the study. The Aim 2 control participants will wear a gold standard cardiac monitor patch (two patches over the 14-days) but will not be offered use of the Pulsewatch system. Please view visual Diagram 1a for an overview of the 14-day participant process.

[figure not shown]

Diagram 1a. Participant process of trial phase: Group names are corresponding to the Part II Consent V1.2 form submitted in eIRB.

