On the day of the participant's scheduled 14-day follow-up visit, a study team member will call the participant and complete the 14-day follow-up questionnaire. Upon completion of the questionnaire, the participant will be randomized into an Aim 3 arm. If the participant is randomized into the control arm for Aim 3, we will ask the participant to mail back all of their Pulsewatch devices via a prepaid package. We will then mail the participant their \$100 gift card. Our normal study protocol will be followed for the rest of these participants study period, which includes conducting a questionnaire over the phone 30 days later and mailing their \$50 gift card.

For participants randomized into the Aim 3 intervention arm, we will ask them to mail back their Cardiac Insight patches via a prepaid package. If the participant was in Aim 2 control and is now in Aim 3 intervention, we will mail them the Pulsewatch System and the AliveCor Kardia Mobile device. We will also mail them their \$100 gift card. If the participant was in Aim 2 intervention and is now in Aim 3 intervention, we will mail them the AliveCor Kardia Mobile device and their \$100 gift card. Upon receiving their devices, a study team member will conduct a phone call, or a Zoom call, with the participant to train them on their new devices. Our normal study protocol will be followed for the rest of these participants study period, which includes conducting a questionnaire over the phone 30 days later, mailing devices back via a prepaid box, and mailing the participant their \$50 gift card.

For participants who have agreed to complete an exit interview, the interview will take place over the phone upon completion of the participant's 14-day follow-up study visit. The fact sheet for this exit interview will be explained to the participant prior to completing the exit interview. We will include this fact sheet in the package we send to participants before completing their baseline interview, so the participant can have it to reference. If the participant misplaces the fact sheet, we will mail it to them again.

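### The motion-noise algorithm is to be tuned on trial participants with AF and its AF accuracy reported against the same patch, with no held-out data and no stated algorithm version for the Aim 2 results

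*Protocol*

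**What the plan says.** Three places in the protocol treat the algorithms as finished before Part II:

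- The section 9 timeline lists "Refine & Integrate AF, skin contact, & MNA algorithms" under development (Aim 1), not under the evaluation rows for Aims 2 and 3.
- Section 11, Hack-a-thon, describes that meeting as held "to create the final Pulsewatch technology to be deployed in Aims 2 and 3".
- Section 11, Part II Trial Phase, says the trial "will occur after the design and development of the Pulsewatch system (app and watch algorithms) is complete (Part I").

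Section 13, Smartwatch Data, plans further work on trial data: "To fine tune and maximize the accuracy of our MNA algorithm, we will use data collected on AF subjects (Aims 2 and 3"). The comparator is the patch worn at the same time, and the paragraph goes on: "Moreover, we will calculate sensitivity, specificity and accuracy of AF detection using our algorithm when compared to Cardiac Insight patch data".

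The same section puts artifact correction before AF detection. Section 13, AF Detection Analysis, and the SAP's Aim 2 Analysis use the 14-day count of Pulsewatch positive readings as the predictor of patch-determined pAF. That logistic model yields the AUC. The SAP's Aim 2 Power paragraph assumes 90 users, 20% with pAF and an AUC of .90 to .95, and gives a 95% CI width of .14 to .20. The SAP does not mention algorithm tuning.

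**The concern.** An accuracy estimate is unbiased for new patients only if the detector was fixed without using the patients on whom it is tested. Here the artifact step is adjusted on AF participants with the patch as reference, and AF detection is then scored on participants from the same trial against that patch. Nothing in either document separates the two uses: there is no algorithm lock, version rule, train/test split, cross-validation or optimism correction.

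The central hypothesis is high sensitivity and specificity against conventional monitoring. If the published figures come from the tuned version, they describe how well the algorithm fits these participants. They would not describe the device the participants wore, or what a new stroke patient could expect.

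**Working it through.** **1. Number of cases.** From the SAP's Aim 2 Power paragraph: 90 × .20 = 18 pAF cases and 72 non-cases. If all AF users are used for tuning, all 18 cases behind the sensitivity estimate are tuning participants. At participant level, one case gained through tuning moves sensitivity by 1/18 = .056.

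**2. The plan's own precision figure.** Hanley–McNeil variance, with T1 = A/(2 − A) and T2 = 2A²/(1 + A):

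Var = [A(1 − A) + 17(T1 − A²) + 71(T2 − A²)] / (18 × 72)

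- A = .90: T1 = .8182, T2 = .8526. Var = (.0900 + .1391 + 3.0268)/1296 = .002512, SE = .0501, width 2 × 1.96 × SE = .196.
- A = .95: T1 = .9048, T2 = .9256. Var = (.0475 + .0385 + 1.6430)/1296 = .001334, SE = .0365, width = .143.

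The stated .20 and .14 reproduce. The interval covers sampling error only and makes no allowance for tuning on the test data.

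**3. Route from tuning to each result.**

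- *Accuracy figures in Smartwatch Data.* They sit in the tuning paragraph, use the same reference and name no other data. If computed with the tuned version, they are at least partly training-set figures.
- *Aim 2 AUC.* Artifact correction comes before the AF call on each 30-second segment, so it affects the 7-of-10 positive readings, their count and the AUC. This applies only if the readings are regenerated after tuning. Regeneration is feasible: Aim 2 watch data are uploaded by staff after the 14-day visit (section 11), and section 13 shows offline processing of raw watch data. If the deployed version's readings are used, the AUC is untouched.
- *Cut-off.* Reading the best cut-off from the same ROC curve is a separate source of optimism. It affects sensitivity and specificity but leaves the AUC unchanged.

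**4. Size, as illustration only.** The documents do not give the number of tuned settings, their correlation or the tuning criterion. Assume 18 cases against 72 non-cases, binormal scores, equally good settings, and the setting with the highest AUC kept.

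| True AUC | Settings compared | Correlation between settings | Result |
|---|---|---|---|
| .90 | 5 | .95 down to .5 | mean reported AUC .91 to .93 |
| .90 | 20 | .95 down to .5 | mean reported AUC .92 to .95 |
| .85 | 5 to 20 | .9 | .021 to .032 too high |
| .85 | 5 to 20 | .8 | .029 to .044 too high |
| .85 | 10 or 20 | .5 | .053 or .064 too high |

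At true AUC .85, a correlation of .95 to .98 gives only .010 to .022.

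**5. Cost of the alternatives.** A half-sample test set (45 users, 9 cases and 36 non-cases) has a CI width of .28 at AUC .90 and .20 at .95. A locked version keeps all 90 users and the stated .14 to .20.

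**The case against.** The strongest reply is that the tuning paragraph describes a side analysis for engineers. The algorithms are to be embedded in the watch, the system is called final before Aims 2 and 3, and the AUC predictor is built from readings collected from Pulsewatch. On that natural reading the AUC uses the deployed version. The tuned part is also the artifact filter, not the AF classifier, and the one added performance measure named for it is heart-rate error, not participant-level AUC. These points stand. A reader might infer that the AUC is certainly biased, but the documents support this only if retuned readings enter the AUC analysis.

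Other stronger readings also fail:

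- *Early and late participants had different detectors.* Enrolment is rolling, but no section plans software updates to watches during the trial.
- *Tuning on Aim 3 data is impossible because patches go back at day 14.* Aim 3 users come from the Aim 2 participants, all of whom wore patches. The reference to both aims can simply mean Part II participants, with patch data from the Aim 2 period.
- *Nothing checks false positives.* The artifact processing is meant to reduce false AF calls, specificity is planned, and the AUC includes non-cases. What remains is narrower: wearers without AF are outside the stated tuning set.

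The reply does not remove the conflict between sections 11 and 13, or the lack of held-out data for the accuracy figures in the tuning paragraph.

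**Conclusion.** The concern holds in limited form. The protocol says both that the algorithms are complete before the trial and that one of them will be tuned on trial participants. The accuracy figures planned beside that tuning would be optimistic if taken from the tuned version. The Aim 2 AUC is exposed only on the further condition that its readings are regenerated with that version. Neither document excludes this.

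No size can be attached from the documents. A reader might take the simulation to show that a true AUC of .85 would be reported as .90. That needs a correlation of .5 between settings and at least 10 of them, with selection on participant-level AUC, which the protocol does not describe. Nor is the SAP's half-width of .07 to .10 the right yardstick there: at AUC .85 with 18 and 72, T1 = .7391, T2 = .7811, SE = .0594 and the half-width is .116. What does follow from the SAP's inputs is that about 18 cases carry the whole sensitivity estimate, and that its interval would not reveal any optimism.

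**What to change.** 1. Reconcile protocol section 11 (Part II, Trial Phase) with section 13 (Smartwatch Data) on whether the algorithms are fixed before Part II.
2. In section 13 (Smartwatch Data and AF Detection Analysis) and the SAP's Aim 2 Analysis, state that all Aim 2 readings, AUC, sensitivity and specificity use the motion-noise and AF algorithm version locked at the end of Part I. If any watch carried another version, re-run the locked one on the stored PPG.
3. Label any tuning on trial data as a separate, later developmental analysis. Report its accuracy only with participant-level cross-validation, so that no person's segments are in both the tuning and test parts.
4. State that patch-referenced data come from the Aim 2 patch-wearing period.

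The cost is some wording in both documents and, if versions differed, one re-run on stored data. No participants are lost. The headline accuracy may be less favourable than the tuned version's. The rule should be written before the Aim 2 data are examined, because a version chosen afterwards cannot be shown to be independent of the results.
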